1.6.2.4 INCB024360 Clinical Studies

INCB24360-101 has been evaluated in Phase I study conducted by Incyte Corporation in subjects with refractory solid tumors. The study has used a 3+3 dose escalation design, with doses of INCB024360 ranging from 50 mg once daily (QD) to 700 mg twice daily (BID). Three subjects have initiated treatment at 50 mg QD, 4 subjects at 50 mg BID, 3 subjects at 100 mg BID, 6 subjects at 300 mg BID, 11 subjects at 400 mg BID, 5 subjects at 500 mg BID and 4 subjects at 700 mg BID.

INCB024360 has generally been well tolerated. The most common Grade 1 or Grade 2 AEs in $\geq 20\%$ reported have been fatigue, nausea, decreased appetite, vomiting, constipation, abdominal pain, diarrhea, dyspnea, back pain, and cough. The most common Grade 3 or Grade 4 AEs were

abdominal pain, hypokalemia, and fatigue (9.6% each). Despite 1 patient reporting a dose-limiting toxicity (DLT) of radiation pneumonitis at 300 mg BID, additional subjects were enrolled at this dose and no additional DLTs were reported. At 400 mg BID, 1 patient reported a DLT of Grade 3 fatigue, with no additional DLTs at this dose level. Another patient at 400 mg BID developed asymptomatic and transient hypopituitarism after 1 cycle of therapy and was able to continue dosing with INCB024360. Among the 18 subjects treated at either 600 mg or 700 mg BID, no DLTs were observed. Dose escalation was completed based on preliminary pharmacokinetic and pharmacodynamic data, which demonstrated that doses of INCB024360 above 300 mg BID achieved exposures exceeding the IC90 determined in nonclinical models and, in pharmacodynamic assays, reached a plateau for Kyn/Trp levels and ratios. In the final cohort of 600 mg BID, the effect of food on INCB024360 absorption was evaluated. No objective responses were reported. At 2 months, stable disease was seen in 15 patients and lasted \geq 4 months in 7 patients. The main AE reported in subjects receiving more than 2 cycles of INCB024360 has been Grade 1 or Grade 2 fatigue.

In a combination study conducted by Incyte Corporation of INCB024360 and ipilimumab in metastatic melanoma patients, 5 of 7 subjects enrolled at a dose of 300 mg BID of INCB024360 plus 3 mg/kg of ipilimumab, developed Grade 3 or Grade 4 AST and ALT elevations between 2 and 4 cycles of treatment. Only one of these subjects had a bilirubin elevation of Grade 1.

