1.6.3 Sirolimus (used in Exploratory Cohort at Roswell Park ONLY)

Sirolimus is a specific inhibitor of the mammalian target of sirolimus (mTOR complex 1) and is the active metabolite of temsirolimus, which is the first in class mTOR inhibitor approved for use in RCC mTOR inhibitor approved for the treatment of renal cell cancer [25-27]. Sirolimus binds to an intracellular protein (FKBP-12), and the protein–drug complex binds to mTOR to inhibit its kinase activity [25]. In preclinical tumor models, sirolimus inhibited cell proliferation, cell growth, survival pathways, and tumor angiogenesis [28, 29]. Initial clinical studies in cancer patients investigated IV sirolimus administered at dosages that were corrected for body surface area (mg/m²) and were designed to establish tolerability, safety, and pharmacokinetic parameters [30, 31]. When administered as a 30-minute infusion once weekly, sirolimus was well tolerated over a wide range of doses (7.5 mg/m² – 165 mg/m²) [31]. Rash and mucositis/stomatitis were the most frequent drug-related AEs, and thrombocytopenia was the main dose-limiting toxicity. Antitumor activity was observed in heavily pretreated patients, including patients with advanced RCC, who received different doses and schedules) [30, 31]. Overall, the most frequent Grade 3 or Grade 4 mTOR inhibition-related AEs (n = 110) were hyperglycemia (17%), hypophosphatemia (13%), anemia (9%), and hypertriglyceridemia (6%).

The major limitation for combining sirolimus and immunotherapy is that mTOR inhibitors are generally regarded as immunosuppressive via several mechanisms, including the induction of regulatory T-cells. Although sirolimus is thought to have immunosuppressive effects, its effects on the potential inhibition of T-lymphocyte function after repeated daily administrations in euthymic mice showed that T-lymphocyte activity recovered within 24 hours after the discontinuation of treatment.

Sirolimus has been used in patients with HIV and hepatitis undergoing solid organ transplant. In several reports no increased incidence of reactivation of HIV or any other viral infection have occurred.

Recent studies by our group and others show that mTOR inhibition appears to significantly condition tumor bearing hosts for augmented vaccine induced T-cell mediated tumor control) [32,

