1.6.4 Potential Risks and Benefits

1.6.4.1 INCB024360 Potential Risks

There have been no adverse findings in toxicology or safety pharmacology assessments described herein. INCB024360-related changes included an increased incidence of diarrhea in 500 mg/kg/day dogs as well as sporadic emesis. Weak cross reactivity of INCB024360 to the human vasopressin 1a receptor, dopamine receptor and carbonic anhydrase II is not expected to pose a risk to humans. Blood pressure will be monitored in this clinical study and blood electrolytes will also be assessed. In 28-day toxicology studies, Cmax values have exceeded the IC50 for the IDO enzyme (72 nM) by up to 37-fold and the IC50 for the vasopressin 1a receptor by up to 4-fold (13-fold in single dose studies) in the absence of any toxicity, so the risk of unintended pharmacological activity is expected to be low.

Hypothetically, IDO represents an important immune control enzyme and cells expressing IDO are capable of suppressing amplified immune effector responses and promoting immune tolerance under various physiological conditions. Inhibition of IDO using 1-MT has been shown to induce fetal allograft rejection in mice (Munn et al, 1998). Syngeneic, pluripotent bone marrow stem cells, transferred to mice with experimental autoimmune encephalomyelitis, a model of multiple sclerosis, enhanced recovery, prevented relapses and promoted myelin repair through their expression of IDO and this was blocked by administration of 1-MT (Matysiak et al, 2008) and inhibition of IDO by systemic administration of 1-MT at clinical onset significantly exacerbated disease scores in this model (Sakurai et al, 2002). Blocking IDO with 1-MT also aggravated the severity of arthritis and enhanced the immune responses in mice with collagen-induced arthritis (Szántó et al, 2007). Taken together, these studies imply that IDO may be a negative inhibition pathway to control autoimmune diseases. For these reasons, patients with autoimmune disease are excluded from participation in this study and study participants will be closely monitored for signs or symptoms of developing autoimmune or inflammatory disease.

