6.7 Treatment Discontinuation

Upon treatment discontinuation all end of study evaluations and tests will be conducted. All patients who discontinue due to an AE must be followed until the event resolves or stabilizes. Appropriate medical care should be provided until signs and symptoms have abated, stabilized, or until abnormal laboratory findings have returned to acceptable or pre-study limits. The final status of the AE will be reported in the patient's medical records and the appropriate eCRF. If patient terminates study participation prior to study completion, all efforts will be made to complete an early termination visit (within approximately 30 days of last dose). Assessment will include physical exam, vital signs and weight, performance status, labs (CBC/diff, CMP, LDH, Coag if on anticoagulants, con med/AE assessment.

Reasons for treatment discontinuation should be classified as follows:

- Death
- Progressive disease
- Treatment-related toxicity
 - Subjects who experience a DLT will not receive any additional treatment (i.e., will be removed from the study and followed until resolution of their toxicity) and will not receive continued treatment even at a reduced dosage of the INCB024360 product.
 - Persistent toxicity that is unresolved to a grade 2 toxicity, where subsequent treatment cannot be given.
- Toxicity unrelated to treatment
- Investigator judgment

- The Investigator may withdraw a patient if, in his/her judgment, it is in the patient's best interest to do so.
- Noncompliance
- Patient voluntary withdrawal
 - A patient may withdraw from the study at any time, for any reason. If a patient discontinues treatment, an attempt should be made to obtain information regarding the reason for withdrawal.
- Roswell Park's decision.

Patients who are unavailable for follow-up evaluations should be classified as lost to follow-up for 1 of the following reasons:

- Lost to follow-up: For a patient to be considered lost to follow-up, the Investigator must make 2 attempts to re-establish contact with the patient. The attempts to re-establish patient contact must be documented (e.g., certified letter).
- Death: Date and cause of death will be recorded for those patients who die within 30 days after last dose of study drug (telephone contact is acceptable).

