Urinary Pregnancy Test in Females of Childbearing Potential	X																							
Concomitant Medications	X ¹²	X			X		X		X		X		X		X		X		X		X			
Adverse Events	X	X			X		X		X		X		X		X		X		X		X			

Study Event	Baseline ¹	Cycle 1			Cycle 2		Cycle 3		Cycle 4		Cycle 5		Cycle 6		Cycle 7		.1.1 Treatment discontinuation ¹³	3 Months, 6 Months, and 12 Months After Last Vaccine or dose of INCB
		Day 1	Day 2	Day 15	Day 1 ± 3 days	Day 2												

- 1 To be performed within 28 days prior to the first vaccination.
- 2 Positive by either PCR or immunohistochemistry ((archived tissue (**Appendix F**) and/or frozen/fresh tumor tissue (**Appendix G**)). Documented historical NY ESO 1 positive results by IHC **or** PCR **or** serum antibody reactive with ESO are acceptable.
- 3 Refer to **Appendix H**
- 4 Including CT scan abdomen and pelvis, or PET/CT as described in **Section 8.5**; within 28 days prior to first vaccination. If patient early terms, CT will be performed at the PI's discretion.
- 5 Only 3 months and 6 month for those patients who have not experienced disease progression.
- 6 Hematology includes: CBC with auto differential, platelets. PT/INR for patients on anticoagulants.
- 7 Chemistry includes: glucose, urea nitrogen, creatinine, calcium, protein, albumin, bilirubin, AST, ALT, LDH, alkaline phosphatase.
- 8 Pharmacokinetic sampling is dependent upon cohort. Refer to **Section 7.7** for details.
- 9 Tumor markers to be obtained as per standard of care.
- 10 INCB024360 will be administered daily for 7 cycles.
- 11 Refer to **Section 7.5**.
- 12 Medications ongoing within 1 week prior to first dose of study drug.
- 13 Approximately 30 days after last study drug, con meds and AE's will be followed. Telephone contact is allowed.

Table 4 Schedule of Procedures/Observations (Exploratory cohort with Sirolimus-Roswell site ONLY)

Study Event	Baseline ¹	Cycle 1				Cycle 2				Cycle 3				Cycle 4				Cycle 5				^{1,2} Treatment discontinuation ¹²	3 Months, 6 Months, and 12 Months After Last Vaccine or dose of Sirolimus
		Day 1	Day 2	Day 15	Day 1 ± 3 days	Day 2	Day 1 ± 3 days	Day 2	Day 1 ± 3 days	Day 2	Day 1 ± 3 days	Day 2	Day 1 ± 3 days	Day 2	Day 1 ± 3 days	Day 2	Day 1 ± 3 days	Day 2	Day 1 ± 3 days	Day 2			
Informed Consent	X																						
Medical History	X	X		X	X		X		X		X		X		X		X		X		X		
Physical Examination, vital signs and weight	X	X		X	X		X		X		X		X		X		X		X		X		
NY-ESO-1, TIL, PD-L1, and/or LAGE-1 Expression in Tumor Tissue²	X																						

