The Phase IIb component of this trial will consist of a randomized parallel design of $n = 25 + 25 = 50$ patients with treatment arms (i) DEC205mAb-NY-ESO-1 fusion protein (CDX-1401) with adjuvant poly-ICLC and (ii) INCB024360 in combination with the DEC205mAb-NY-ESO-1 fusion protein (CDX-1401) with adjuvant poly-ICLC. Stratification will be on clinical site (Roswell Park, U. of Pittsburgh). The primary endpoint will be progression free survival. Baseline is defined as the time following the treatment free interval, which can span 0 - 2 months, as described in Iasonos et al.[1] The primary analysis will be carried forth using a Cox proportional hazards model with factors corresponding to treatment and a continuous covariate adjustment for the length of the treatment free interval and a stratification factor for clinical site. Permuted blocked random assignment with block sizes of 4 and an allocation ratio of 1:1 for DEC205mAb-NY-ESO-1 fusion protein (CDX-1401) with adjuvant poly-ICLC alone versus INCB024360 in combination with the DEC205mAb-NY-ESO-1 fusion protein (CDX-1401) with adjuvant poly-ICLC stratified by clinical site..

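### Apart from calcium, the scheduled chemistry panel lists no electrolytes, and potassium appears at no scheduled visit, although the protocol says electrolytes will be assessed

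*Combined protocol and SAP*

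**What the plan says.** Four places in the combined protocol and SAP bear on electrolytes.

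- **Section 1.6.4.1 (INCB024360 risks)**, after describing weak cross-reactivity with the vasopressin 1a receptor, a dopamine receptor and carbonic anhydrase II: "Blood pressure will be monitored in this clinical study and blood electrolytes will also be assessed". It names no analytes or visits.
- **Section 1.6.2.4 (clinical experience with INCB024360)** gives the leading Grade 3-4 events as "abdominal pain, hypokalemia, and fatigue (9.6% each". It does not say how many were attributed to drug.
- **Section 7.3, footnote 7 of Table 3**, repeated word for word under Table 4: "Chemistry includes: glucose, urea nitrogen, creatinine, calcium, protein, albumin, bilirubin, AST, ALT, LDH, alkaline phosphatase".
- **Section 6.7 (treatment discontinuation)** lists "labs (CBC/diff, CMP, LDH, Coag if on anticoagulants" for one visit, which is conditional: "If patient terminates study participation prior to study completion, all efforts will be made to complete an early termination visit". CMP is not defined in the documents.

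Section 9.1.1.3 also illustrates how to record a laboratory adverse event with a serum potassium of 7 mEq/L.

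**The concern.** The risk section makes a monitoring commitment in two halves. The blood-pressure half appears in the schedule, because vital signs have their own row in Tables 3 and 4. The electrolyte half does not, apart from calcium. A site working from the tables would find no instruction to measure potassium, although the protocol's own clinical experience puts hypokalemia among the most frequent severe events with the drug.

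At stake is safety ascertainment in Phase IIb. Section 6.3 bases INCB024360 dose modification on Grade 3 or higher treatment-related toxicity outside the DLT period. Section 6.3.2 pauses the study for data review after any Grade 4 event. Section 11.5 relies on review of changes in laboratory values. An abnormality that causes no symptoms reaches these rules only if someone measures it. The trial is open-label and Section 7.2 leaves unscheduled visits to the investigator's discretion, so unscripted testing could also differ between arms or sites. That would blur a comparison of laboratory events.

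**Working it through.** The point rests on comparing sections. The plan gives no electrolyte figure to reproduce.

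**Step 1: what the panel contains.** Footnote 7 lists 11 analytes. Checked against sodium, potassium, chloride, bicarbonate, magnesium, phosphate and calcium, only calcium is present.

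**Step 2: whether another row supplies the rest.** The other laboratory rows in Table 3 are hematology with PT/INR, tumor markers, pharmacokinetic/pharmacodynamic sampling, immune response, HLA typing and the pregnancy test. Table 4 drops the pharmacokinetic row and adds CMV PCR and a lipid profile. None includes potassium, sodium, chloride or bicarbonate.

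**Step 3: whether another section supplies the rest.** Section 6.7 names a CMP. In usual use that panel includes sodium, potassium, chloride and bicarbonate; this is an assumption, since the protocol does not define it. The early termination visit is not a separate column in Tables 3 and 4, and it applies only to patients who leave before completion. A patient who completes treatment has no listed potassium measurement.

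**Step 4: scale, for illustration.** Inputs: 9.6% Grade 3-4 hypokalemia (Section 1.6.2.4) and 25 patients in Cohort 2b (Table 1 and Section 11.1).

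- Expected cases: 25 x 0.096 = 2.4.
- Chance of at least one: 1 - (1 - 0.096)^25 = 1 - 0.904^25 = 0.92.

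These are all-cause figures and assume that the rate carries over. To show how they depend on that assumption:

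| Assumed rate | Expected cases in 25 | Chance of at least one |
|---|---|---|
| 9.6% | 2.4 | 0.92 |
| 4.8% (half) | 25 x 0.048 = 1.2 | 1 - 0.952^25 = 0.71 |
| 2.4% (a quarter) | 25 x 0.024 = 0.6 | 1 - 0.976^25 = 0.46 |

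The denominator behind 9.6% is not fully shown. The doses listed in Section 1.6.2.4 account for 3 + 4 + 3 + 6 + 11 + 5 + 4 = 36 patients. The 18 patients at 600 or 700 mg, less the 4 at 700 mg, imply 14 more, which makes 50. Yet 5/50 = 10.0%, while 5/52 = 9.6%. This does not affect the comparison in Steps 1 to 3.

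**The case against.** The best defence is that footnote 7 says what chemistry includes, which need not be exhaustive. The CMP in Section 6.7 and the potassium example in Section 9.1.1.3 suggest that the authors expected potassium results, and a local laboratory may report them routinely. Part of this stands: the list cannot be called closed, and one cannot say that potassium will never be measured. But the hematology and lipid footnotes use similar wording to define their panels, and a list that spells out protein, albumin and LDH reads as a definition. Nothing tells a site to add potassium.

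A reader might also infer more than the documents support:

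- *That no electrolytes are measured.* Calcium is listed.
- *That hypokalemia is a risk named in Section 1.6.4.1.* It is not. It appears under clinical experience, and Section 1.6.4.1 says the cross-reactivity is not expected to pose a risk to humans.
- *That 2.4 events estimates missed dose modifications.* Section 6.3 requires a treatment-related event, and the 9.6% carries no attribution. It also comes from refractory solid tumors over a wide dose range, whereas patients here are in remission or have minimal residual disease.
- *That the INCB024360 dose choice is in doubt.* Table 1 and Section 6.3 record that Phase I review is complete and the Phase IIb dose selected. The live effect is on Phase IIb.
- *That the safety rules cannot operate.* Unscheduled visits, ongoing safety review and the early termination CMP all remain. Section 9.1.1.3 also limits recording to clinically significant abnormalities that need active management.
- *That phosphate is wrongly missing for the sirolimus cohort.* Section 1.6.3 does report Grade 3-4 hypophosphatemia at 13%, but it follows an account of intravenous dosing, while this cohort takes oral tablets at a fixed daily dose. No section promises phosphate monitoring, so there is no contradiction to resolve.

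**Conclusion.** The inconsistency is real and should be fixed. Section 1.6.4.1 says electrolytes will be assessed, while the schedule lists calcium alone. Potassium, the analyte behind one of the three most common Grade 3-4 events reported with INCB024360, is listed for no visit in Tables 3 and 4.

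The consequence is possible under-detection of asymptomatic abnormalities in Phase IIb and a reported rate that may be too low. How low cannot be estimated, because the documents do not show how often sites would measure potassium anyway. The 2.4 expected cases and 92% indicate scale only; they are all-cause and assume that 9.6% applies to this population. They bear most directly on adverse event reporting, since Table 8 asks for Grade 3-4 events in Phase IIb whatever their attribution.

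The finding concerns safety ascertainment. It does not touch the primary endpoint, the Cox model or the sample size.

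**What to change.** Reconcile Sections 1.6.4.1, 6.7 and 7.3. The simplest way is to amend footnote 7 in both tables so that the panel names sodium, potassium, chloride and bicarbonate at the draws where chemistry is already scheduled, or to replace the list with a defined CMP plus LDH, matching Section 6.7. Table 3 is the only schedule that covers Phase IIb, so one change there gives both randomized arms the same ascertainment. Define CMP once, so that the schedule and the early termination visit mean the same panel.

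The cost is one footnote in each table and a small laboratory charge, with no added visit or venipuncture. A few more laboratory adverse events may be recorded. If the sponsor does not intend to measure electrolytes routinely, the sentence in Section 1.6.4.1 should be revised to say so, with a reason that addresses the hypokalemia figure in Section 1.6.2.4.

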7.4 Pathology

7.4.1 Baseline Tumor Tissue Requirements

Tumor tissue requirements for IDO, NY-ESO-1, TIL, PD-1, PD-L1 and/or LAGE-1, Expression in Tumor are as follows:

- Evaluation of NY-ESO-1 will occur at OmniSeq.
 - 5 unstained sections (5 μ m thick) and 8 tissue curls (10 μ m thick) cut with molecular precautions.
- Evaluation of all other biomarkers will occur in the Pathology Network Shared Resource at Roswell Park.
 - 8 unstained sections (5 μ m thick) on plus glass
- Evaluation by PCR will occur in Immune Analysis Facility at the Center for Immunotherapy at Roswell Park. The director of the center is [name], Cancer Cell Center, Roswell Park, Room C-410, [contact], e-mail address, [contact]. Refer to **Appendix G**.
 - This will be performed when fresh/frozen tumor tissue is available.
- Documented historical NY ESO 1 positive results by IHC or PCR or serum antibody reactive with ESO are acceptable.

Network Site see Appendix J for specific instruction.

Note: All investigator or analyzing research laboratories housing research samples need to maintain current Temperature Logs and study-specific Sample Tracking and Shipping Logs. The Principal Investigator/Laboratory Manager must ensure that the stated lab(s) have a process in place to document the receipt/processing/storage/shipping of study-related samples/specimens. This is required for both observational and interventional clinical studies collecting clinical samples.

7.4.2 Recurrence Tumor Tissues Requirements

The standard of care in patients who develop recurrent cancer, for the most part, is an additional cytotoxic chemotherapy. In order to ascertain whether treatment failure is a consequence of antigenic loss or represents failure of this strategy, it will be important to analyze tissue specimens from patients with recurrent disease. In a subset of patients, surgical resection of recurrent/progressive disease will be indicated as part of standard care. Specimens obtained at the time of surgery for recurrent/progressive disease will be analyzed for antigen expression and antigen-specific tumor infiltrating lymphocytes. The basic panel of markers noted in **Section 7.4.1** will also be tested. Up to 25 unstained sections of formalin-fixed paraffin-embedded recurrent tumors cut at 5 μ m thickness on plus slides from the same population of patients will be used. The paraffin-embedded archival specimens will be obtained from the paraffin-archive resource in Roswell Park's Department of Pathology. Fresh or frozen tumor tissue will be obtained from Roswell Park Protocol I 115707 titled "Roswell Park Remnant Clinical Biospecimen Storage,

Collection, and Distribution for Research Purposes”, or I 215512 titled “Analysis of Tumor Antigens, Immunity, and Genetic Changes in Gynecological Cancer Patients”.

